7.4 Serious Adverse Event Reporting

Within 24 hours of awareness of a serious adverse event, whether or not related to the study drug, the investigator will complete and submit a Medwatch 3500a form, containing all required information (reference CFR § 312.32). The investigator will submit a copy of this Medwatch 3500a form to the sponsor-investigator and Esanik by either e-mail or fax, within the same timeframe.

The SAE documentation, including the Medwatch 3500A form and available source records should be emailed or faxed to:

Email: [contact]

[contact]

The following minimum information is required:

- study number
- subject number, sex and age
- the date of report
- a description of the SAE (event, seriousness of the event)
- causal relationship to the study drug. Follow-up information for the event should be sent within 7 days as necessary. Copy of above should also be sent to coordinating site (PI- [name]).

Sponsor-Investigator:

[name] FACP
[name]
[name]

[contact]
[contact]
Email: [contact]

7.4.1 Safety Reporting Requirements for IND Holders

In accordance with 21 CFR § 312.32, sponsor-investigators of studies conducted under an IND must comply with following safety reporting requirements:

Expedited IND Safety Reports:

7.4.2 Calendar-Day Telephone or Fax Report:

The Sponsor-Investigator is required to notify the FDA of any fatal or life-threatening adverse event that is unexpected and assessed by the investigator to be possibly related to the use of ESK981. An unexpected adverse event is one that is not already described in the Investigator Brochure. Such reports are to be telephoned or faxed to the FDA within 7 calendar days of first learning of the event. Each telephone call or fax transmission (see fax number below) should be directed to the FDA new drug review division in the Center for Drug Evaluation and Research or in the product review division for the Center for Biologics Evaluation and Research, whichever is responsible for the review of the IND.

15 Calendar-Day Written Report:

The Sponsor-Investigator is also required to notify the FDA and all participating investigators, in a written IND Safety Report, of any serious, unexpected AE that is considered possibly related to the use of ESK981. An unexpected adverse event is one that is not already described in the Investigator Brochure.

Written IND Safety Reports should include an Analysis of Similar Events in accordance with regulation 21 CFR § 312.32. All safety reports previously filed with the IND concerning similar events should be analyzed. The new report should contain comments on the significance of the new event in light of the previous, similar reports.

Written IND safety reports with Analysis of Similar Events are to be submitted to the FDA, Esanik Drug Safety, and all participating investigators within 15 calendar days of first learning of the event. The FDA prefers these reports on a MedWatch 3500a Form but alternative formats are acceptable (e.g. summary letter).

FDA fax number for IND Safety Reports:

[name]

IND Annual Reports

In accordance with the regulation 21 CFR § 312.32, the Sponsor-Investigator shall within 60 days of the anniversary date that the IND went into effect submit a brief report of the progress of the investigation. Please refer to Code of Federal Regulations, 21 CFR § 312.32 for a list of the elements required for the annual report. All IND annual reports submitted to the FDA by the Sponsor-Investigator should be copied to Esanik.

7.5 Procedure in Case of Pregnancy

The effect of ESK981 in pregnant and lactating women is not known, and the exposure of a fetus or nursing infant is considered a potential risk. ESK981 can cause fetal harm when administered to a pregnant woman based on its mechanism of action. Subjects receiving ESK981 are advised to use two acceptable methods of birth control (one of which must include a condom as a barrier method of contraception) starting at the time of screening for an ESK981 study and continuing throughout the course of treatment and for at least three months after ESK981 is discontinued.

If, during the conduct of the clinical trial, a male subject impregnates his partner, the subject should report the pregnancy to the investigator. The investigator should report the pregnancy to the sponsor as an SAE within 24 hours of awareness of the event. The expected date of delivery or expected date of the end of the pregnancy, last menstruation,

estimated fertility date, pregnancy result and neonatal data etc., should be included in this information.

The investigator should report the outcome of the pregnancy (independent of outcome, e.g., full term delivery, pre-term delivery, spontaneous abortion, induced abortion, stillbirth, death of newborn, congenital anomaly [including anomaly in a miscarried fetus, etc.]) in accordance with the same reporting procedure as for SAEs. The date of outcome of the pregnancy, gestational age, date of birth and neonatal data etc., should be included in this information.

8. CRITERIA FOR OUTCOME ASSESSMENT/THERAPEUTIC RESPONSE

8.1 Outcome Assessment

All baseline evaluations will be performed as closely as possible to the beginning of treatment (<4 weeks). For subsequent evaluations, the method of assessment and techniques will be the same as those used at baseline.

8.1.1 Measurement of clinical lesions

Only superficial clinical lesions (e.g., skin nodules and palpable lymph nodes) are considered measurable. In the case of skin lesions, documentation by color photography, including a ruler to estimate the size of the lesion, is recommended.

8.1.2 Chest x-ray

Lesions on chest x-ray are acceptable as measurable lesions when they are clearly defined and surrounded by aerated lung; however, CT is preferable to x-ray.

8.1.3 Conventional CT, MRI, positron emission tomography (PET), bone scan

To assess the antitumor effect of a treatment, imaging-based evaluation is preferable to evaluation by clinical examination. CT and MRI should be performed using contiguous slices of 10 mm or less. Spiral CT should be performed using a 5-mm contiguous reconstruction algorithm (interval). If a 5-mm contiguous reconstruction algorithm (interval) is not used, as a general rule, the lesion diameter should be no less than double the reconstruction algorithm (interval) and must be at least 20 mm for a nonspiral CT or at least 10 mm for spiral CT. (If available, spiral CT is preferred in all instances.) A technetium-99m bone scan will be performed at screening and at each tumor assessment during the study to evaluate bone metastasis. For adequate assessment of bone lesions, it is expected that the radiologist will adjust window leveling accordingly. PET scan will be used for bone scan if requested by physician. This applies to tumors of the chest, abdomen, pelvis and bone. Head and neck tumors and those of the extremities typically require specific protocols.

8.1.4 Ultrasound

When the primary endpoint of the study is objective response, ultrasound should not be used to measure tumor lesions. Ultrasound may be appropriate, however, as a possible alternative to clinical measurements of superficial, palpable lymph nodes, subcutaneous lesions, or thyroid nodules, or to confirm the complete disappearance of superficial lesions (usually assessed by clinical examination).

8.1.5 Endoscopy/laparoscopy

Using endoscopy or laparoscopy for objective tumor evaluation has not yet been fully validated and should be restricted. These techniques may be useful, however, to confirm complete pathological response when biopsies are obtained.

8.1.6 Tumor markers

Tumor markers alone cannot be used to assess response. If markers are initially above the ULN, they must normalize for a patient to be considered in complete clinical response.

8.1.7 Cytology/histology

In certain situations, cytology and histology can be used to differentiate response (e.g., residual lesions in tumor types, such as germ cell tumors, where known residual benign tumors can remain). When the measurable tumor has met criteria for response or stable disease, cytological confirmation of the neoplastic origin of any effusion that appears or worsens during treatment is mandatory to differentiate between response, stable disease, and progressive disease.

8.2 Therapeutic Response

Response and progression will be evaluated in this study using a combination of the revised Response Evaluation Criteria in Solid Tumors (RECIST 1.1) criteria¹⁵ and the guidelines for prostate cancer endpoints developed by the Prostate Cancer Clinical Trials Working Group (PCWG3).³

Trial objectives are defined based on controlling, relieving, or eliminating disease manifestations that are present when treatment is initiated, or preventing or delaying the development of disease manifestations that are expected to occur (or in some cases both). Identify whether control/relieve/eliminated or prevent/delay endpoints. Traditional measures of response reflect when a treatment is working and measures of progression indicate when a drug should be stopped. Because assessing response in bone (the most common site of prostate cancer spread) is uncertain and the clinical significance of PSA changes in response to therapy is not a reliable predictor of response, measures of response have been expanded in consortium trials to include measures of progression.

Patients will need to be reevaluated for response every cycle (or more frequently if indicated), according to the guidelines below.

8.2.1 PSA

In this study, PSA testing is being performed on days 8, 15, and 22 of Cycle 1, Day 1 of Cycle 2 and each subsequent cycle (every 4 weeks) with the threshold PSA level at 2.0 ng/mL. To report PSA-based outcomes, PCWG3 recommends that the percent of change in PSA from baseline to 8 weeks (or earlier for those who discontinue therapy) and the maximum decline in PSA that occurs at any point after treatment be reported for each patient using a waterfall plot.³ Because the rate of rise has shown prognostic significance, estimate a pretreatment PSA doubling time (PSA-DT) if at least 3 values are available, but do not delay either treatment or enrollment onto a trial simply to estimate PSA-DT. Because declines in serum PSA, if they occur, may not do so for several weeks, PSA measurements obtained during the first 8 weeks should not be used as the sole criterion for clinical decision making.

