3.1 Inclusion Criteria

Patients should meet all of the following criteria at the time of registration:

- 3.1.1 Have signed an informed consent document indicating that the subject understands the purpose of and procedures required for the study and are willing to participate in the study.
- 3.1.2 Be willing and able to adhere to the prohibitions and restrictions specified in this protocol.
- 3.1.3 Males 18 years of age and above.
- 3.1.4 Eastern Cooperative Group (ECOG) performance status ≤ 1 .
- 3.1.5 Patient must have progressive disease while receiving androgen deprivation therapy (ADT) defined by any one of the following as per the PCWG3 criteria for PSA, measureable or non-measurable (bone) disease and must have a castrate serum testosterone level (i.e. ≤ 50 ng/dL) at screening:
 - 3.1.5.1 PSA: At least two consecutive rises in serum PSA, obtained at a minimum of 1-week intervals, with the final value ≥ 2.0 ng/mL.
 - 3.1.5.2 Measurable disease (by RECIST 1.1): $\geq 20\%$ increase (with an absolute increase of at least 5mm) in the sum of diameters of all measurable lesions or the development of one or more new lesions. The short axis of a target lymph node must be more than 15mm to be assessed for change in size.
 - 3.1.5.3 Non-measurable (bone) disease: The appearance of two or more new areas of uptake on bone scan consistent with metastatic disease compared to previous imaging during castration therapy. The increased uptake of pre-existing lesions on bone scan will not be taken to constitute progression, and ambiguous results must be confirmed by other imaging modalities (e.g. X-ray, CT or MRI).
- 3.1.6 Documented histologically confirmed adenocarcinoma of the prostate.
- 3.1.7 Metastatic prostate cancer (M1) as documented by appropriate medical imaging (i.e. CT-Scan, PET scan or bone scan).

- 3.1.8 Treatment failure of either abiraterone and/or enzalutamide per PCWG3 criteria for PSA, measurable disease or non-measurable (bone) disease.
- 3.1.9 Willingness to use contraception by a method that is deemed effective by the Investigator throughout the treatment period and for at least 30 days following the last dose of therapy.
- 3.1.10 Willingness and ability to comply with study procedures and follow-up examination.
- 3.1.11 Able to swallow and retain oral medication.
- 3.1.12 Willingness and ability to undergo mandatory tumor biopsy at baseline and week 8/cycle 3.

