8.3.4 PSA Response

As long as patient safety is the primary concern, in the absence of other indicators of disease progression, therapy should not be discontinued solely on the basis of a rise in PSA after week 8.

PSA progression is defined as the date that a 25% or greater increase and an absolute increase of 2.0 ng/mL or more from the nadir is documented and confirmed by a second value obtained 3 or more weeks later. Where no decline from baseline is documented, PSA progression is defined as a 25% increase from the baseline value along with an increase in absolute value of 2.0 ng/mL or more after 8 weeks.

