9.4 Metastatic Kinome Activity Profiles as Predictive Biomarkers for Response to ESK981

Since the mechanism of ESK981 is based on the multiplex inhibition of a set of protein kinases we hypothesize that a tumor's dependence on kinase signaling pathways (kinome activity profile) will correlate with sensitivity to multiplex kinase inhibition by ESK981. Similarly, kinome activity profiles will be quantified through the expression levels of individual tyrosine and serine/threonine kinases targeted by ESK981 and, by proxy of gene expression signatures, the activity of their downstream signaling pathways. The activity of each targeted kinase will be correlated with the clinical endpoints independently, and in conjunction with the tumor's AR status and other genetic alterations.

9.5 Evaluation of Circulating and Disseminated Tumor Cells as Pharmacodynamic Biomarkers of ESK981 response.

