11.2 Endpoints

11.2.1 The first primary endpoint (PSA50) is a PSA decline of $\geq 50\%$ from baseline (PSA50), using the PCWG3 criteria. Refer to Section 8.2.1.

The second primary endpoint(s) (toxicities) is (are) defined in Section 7. Adverse events of all grades will be captured by the National Cancer Institute - Common Terminology Criteria for Adverse Events, version 4.03 (NCI-CTCAE v4.03) and GCP standards.

11.2.2 The secondary endpoints are defined as follows:

Time to PSA response (TTPR) is defined as the time from treatment start until the first documented occurrence of PSA50. PSA50 is defined in Section 1.3.

Duration of PSA response (PRD) is defined as the time from start of PSA50 until PSA progression (defined in Section 8.3.2).

PSA progression free survival (PPFS) is defined in Section 8.3.2 except that it will be based on PSA assessments only. PSA progression rates will be estimated from the PSA-only PFS distribution.

11.2.3 The correlative/exploratory/tertiary endpoints (and the methods of their determination) are described in Section 9.

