11.4 Analysis

11.4.1 For the Primary Objectives, all analyses point and (1-sided Wilson type 90% lower) CI estimates of the primary endpoint (PSA50) will be calculated.

Adverse events will be tabulated by incidence and severity graded according to the National Cancer Institute – Common Terminology Criteria for Adverse Events (CTCAE) version 4.03. Other statistics will include point and (2-sided) CI estimates of overall toxicity and of specific types of toxicity.

11.4.2 For Secondary Objective 1, descriptive statistics of TTPR will be used to summarize the time to PSA response. These descriptives will include N, median, mean, standard deviation (SD), interquartile range (IQR), minimum, and maximum.

11.4.3 For Secondary Objectives 2 and 3, the censored distributions of duration of response (RD) and PSA progression free survival (PFS) will be summarized with the Kaplan-Meier (K-M) survivorship estimate. A graph of the K-M curve for PRD and for PPFS will be generated along with the Hall-Wellner 90% confidence band, and a display of the number of patients at risk at several time points, below the X-axis. Summary statistics (6-month rate, 12-month rate, median, etc.) will be calculated from the K-M life table, each one with its respective 80% confidence interval (CI).

11.4.4 For the Correlative (Exploratory) Objectives, frequency distributions of all categorical variables (grade of specific types of toxicity, and categorical biomarkers or other correlatives) will be generated. Serial PSA levels will be displayed using spaghetti plots, and changes in PSA using waterfall plots.

Descriptive statistics will be used to summarize all continuous correlatives (e.g., PSA, continuous biomarkers and other correlatives), and changes in them pre/post ESK981 treatment. Gene expression levels will be \log_2 transformed prior to descriptive analysis. Multiple boxplots and scatterplots will be used to display summary statistics of biomarkers/correlatives and interrelationships between continuous correlatives, respectively.

Details of the planned determination of bioinformatics correlatives are given in Section 9. Response (whether PSA50 or overall), a categorical clinical outcome, will be statistically modeled as a function of each correlative using exact logistic regression. TTPR, a continuous

uncensored clinical outcome (limited to only the PSA50 responders), will be statistically modeled as a function of each correlative using linear regression.

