Time to event clinical outcomes (PRD and PPFS) will be statistically modeled as a function of each correlative using Cox proportional hazards regression. Examples of categorical correlatives include: gene mutation status (Sec. 9.1 and 9.2); AR dependence (Sec. 9.3); and vacuolization status or vascularization status (Sec. 9.6). Examples of continuous correlatives include: kinase expression levels (Sec. 9.4); CTC and DTC counts (Sec. 9.5); and levels of Ki67, AR, and LC3 (Sec. 9.6).

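### Pretreatment PSA doubling time is to be estimated because it is prognostic, but no analysis uses it, so the unadjusted PPFS biomarker models can pick up prior PSA growth

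*Combined protocol and SAP*

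**What the plan says.** Section 8.2.1 (PSA) states: "Because the rate of rise has shown prognostic significance, estimate a pretreatment PSA doubling time (PSA-DT) if at least 3 values are available". The estimate is conditional on three values, and neither treatment nor enrolment is to wait for it. PSA-DT does not appear again in the objectives (Section 2), the correlatives (Section 9) or the statistical section (Section 11).

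Section 11.4.4 sets out the biomarker models: "Time to event clinical outcomes (PRD and PPFS) will be statistically modeled as a function of each correlative using Cox proportional hazards regression". Response "will be statistically modeled as a function of each correlative using exact logistic regression". Neither names a baseline covariate. The only joint analysis mentioned is in 9.4, where kinase activity is to be examined on its own and also "in conjunction with the tumor's AR status and other genetic alterations".

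On the endpoint, 11.2.2 says: "PSA progression free survival (PPFS) is defined in Section 8.3.2 except that it will be based on PSA assessments only". Section 8.3.2 concerns non-target lesions. The PSA rule stands in 8.3.4, and I take that to be meant. After a decline, the rule reads: "PSA progression is defined as the date that a 25% or greater increase and an absolute increase of 2.0 ng/mL or more from the nadir". Confirmation is needed at least 3 weeks later. Without a decline, "PSA progression is defined as a 25% increase from the baseline value along with an increase in absolute value of 2.0 ng/mL or more", counted after 8 weeks.

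The design has one arm (11.3.1). Section 9 labels the correlative work tertiary or exploratory. Even so, 9.3 hypothesises that loss of AR dependence is an independent predictor, and the heading of 9.4 calls kinome profiles predictive biomarkers.

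**The concern.** PPFS ends when PSA has risen by a set amount. If the growth seen before treatment persists even in part, men with fast prior growth reach the endpoint sooner whatever the drug does. A marker that travels with growth rate (a proliferation marker such as Ki67 is a natural candidate) is then associated with PPFS through prognosis alone. There is no control arm against which to see this, and the planned model contains nothing that would absorb it. The protocol itself names the relevant baseline variable and says why it matters, then leaves it out of the analysis.

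At stake is how the Section 9 results are read: which markers are carried forward, and whether an association is reported as saying something about ESK981.

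**Working it through.** **1. The plan's own figures.** The plan gives no figure for the correlative models, so the checks use its N. Section 11.3.2 states N = 27, an estimate of 30% and a one-sided 90% Wilson lower limit of 0.201. With z = 1.2816:

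(0.30 + 1.6424/54 − 1.2816 × √(0.21/27 + 1.6424/2916)) / (1 + 1.6424/27) = 0.2134/1.0608 = 0.2011.

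This reproduces. So does enrolment: 27/0.85 = 31.8, rounded up to 32. Expected responders: 0.30 × 27 = 8.1.

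**2. Link between prior growth and PPFS.** Under steady exponential growth, time to a 25% rise = log2(1.25) × PSA-DT = 0.322 × PSA-DT. PSA is read on Day 1 of each 4-week cycle after Cycle 1 (8.2.1), and a rise without prior decline counts only after 8 weeks (8.3.4). The doubling times below are illustrative.

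| PSA-DT (months) | Time to +25% (months) | Weeks (× 4.345) | First countable visit if week 8 counts | If it does not |
|---|---|---|---|---|
| 1.5 | 0.48 | 2.1 | week 8 | week 12 |
| 3 | 0.97 | 4.2 | week 8 | week 12 |
| 6 | 1.93 | 8.4 | week 12 | week 12 |
| 12 | 3.86 | 16.8 | week 20 | week 20 |

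The crude times span 3.86/0.48 = 8-fold. The observable times span 20/8 = 2.5-fold or 20/12 = 1.7-fold. The 2.0 ng/mL minimum also governs whenever the reference PSA is below 2.0/0.25 = 8 ng/mL. The link is real but weakened, most of all for fast growers.

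**3. False-signal rate.** Each simulation has 27 men and a marker with no effect of its own, correlated (rho) with pretreatment growth. Entries are the share of trials with two-sided p < 0.05 in the Cox model, without and then with log PSA-DT. No alpha for correlatives is stated in the plan; 0.05 is assumed.

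| Run | Assumptions (none from the documents) | rho 0.5 | rho 0.7 |
|---|---|---|---|
| A | inert drug, 8.3.4 on the protocol schedule, median PSA-DT 4 months, log-SD 0.5–0.8, PSA CV 12% | 12–14% → 2–3% | 18–30% → 4% |
| B | drug halves growth in all men, median PSA-DT 3 months, log-SD 0.8, other log-time noise SD 0.5, 4-weekly visits from week 12, censoring at 52 weeks | 38% → 1% | 72% → 2% |
| C | inert drug, 8.3.4 on schedule, log-SD 0.8, median baseline PSA 30, true PSA-DT known | 17% → 4% | 30% → 2% |
| D | inert drug, 8.3.4 on schedule, log-SD 0.8, PSA-DT known or from values 8–12 weeks apart | 7–9% → 3–4% | 11–16% → 3–4% |

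Runs A and B used 600 trials per setting and C used 400. The Monte Carlo standard error at a 5% rate is √(0.05 × 0.95/600) = 0.9 points, or 1.1 points with 400.

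Sensitivity of B at rho 0.5, unadjusted: 13% with median PSA-DT 1.5 months (most events tie at the first countable visit), 50% with 6 months; 47% with noise SD 0.25, 17% with noise SD 1.5. At rho 0, B gave 5% unadjusted and 1% adjusted. Its adjusted test is therefore conservative with so few visit times, and 1–2% is not better than nominal performance. With exact event times and a noisy PSA-DT, B gave 55% → 10% at rho 0.5. The adjusted rate there was already 9% at rho 0, so little of that remainder comes from the correlation.

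**4. Quality of the PSA-DT available.** Entry by PSA requires "At least two consecutive rises in serum PSA, obtained at a minimum of 1-week intervals". With three values d weeks apart and a log-scale SD of 0.12, the fitted change over the span 2d has SE = 0.12 × √2 = 0.17 whatever d is. With PSA-DT 4 months (17.4 weeks), the true change is 0.693 × 2d/17.4:

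| Spacing | True log change | Ratio to SE |
|---|---|---|
| 1 week | 0.08 | 0.5 |
| 4 weeks | 0.32 | 1.9 |
| 8 weeks | 0.64 | 3.8 |
| 12 weeks | 0.96 | 5.6 |

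The simulations agree. With values 1 week apart, C gave 18% → 17% (rho 0.5) and 27% → 28% (rho 0.7), which is no benefit, and D also showed no fall. With values 4 weeks apart, C gave 15% → 8% and 29% → 12%, and D's adjusted rates were 6–9%.

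**5. Power.** For a real marker effect at rho 0, power was 20% without and 20% with adjustment. In a separate run (log-SD 0.5), adjusted power was 19% at rho 0, 13% at rho 0.5 and 8% at rho 0.7.

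**The case against.** The strongest reply has four parts.

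- **The work is exploratory.** No alpha or decision rule is attached to these models. This stands and limits the stakes. It does not settle the matter, because 9.3 and 9.4 use the language of independent and predictive markers.
- **The covariate may be missing or poor.** PSA rise is one of three entry routes (3.1.5), and no proportion by route is given. Men entering that way have at least three values, but these may be a week apart, when adjustment achieves nothing. The calendar in Appendix C lists no collection of historical PSA values. This stands, and it is why the adjusted model should sit beside the single-marker model and not replace it.
- **Adjustment costs power where confounding exists.** A reader might infer from the rho 0 result that it is free. Step 5 shows that it is not. PSA events may also be fewer than 27, since men leave for symptomatic or objective progression (5.1).
- **One arm cannot separate prognosis from prediction.** This is correct with or without PSA-DT. Adjustment removes one known source of confounding and no more.

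A reader might also say that choosing PSA-DT over other prognostic variables is a matter of taste. Here the protocol makes the choice itself, in 8.2.1.

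**Conclusion.** The gap is real. PSA-DT is to be estimated for its prognostic value, no analysis uses it, and the Cox models for a PSA-rise endpoint carry no baseline covariate. A marker that only tracks prior growth can reach p < 0.05 more often than 5% of the time. At rho 0.5 the main settings give roughly 7% to 40%. Single sensitivity settings reached 50% with 4-weekly visits and 55% with exact event times. At the low end the excess over 5% is small. The correlations, the PSA-DT distribution and the noise are all assumed.

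Three stronger readings are not supported. A reader might infer that such markers will look like predictors; at rho 0.5 most simulated trials under the main settings showed nothing. A reader might take the 8-fold spread in crude time to a 25% rise as the spread in PPFS; the 8-week rule and the visit schedule cut it to about 1.7- to 2.5-fold in the example. A reader might conclude that a marker surviving adjustment predicts ESK981 benefit; a trial without controls cannot show that.

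The point concerns the exploratory analyses only.

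**What to change.** In 11.4.4, prespecify for the PPFS Cox models a second model with the marker plus log pretreatment PSA-DT, reported beside the single-marker model. Fit it in men with at least three pretreatment PSA values. Report how many men have it and the span of their values, and give the unadjusted result in the same men, so that a change in the estimate is not confused with a change in the sample.

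Leave the exact logistic models as they are: about 8 responders will not carry a second term. Describe the associations, including those under 9.3 and 9.4, as prognostic or hypothesis-generating. While editing, point the PPFS and PRD definitions in 11.2.2 to 8.3.4.

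Cost: a few lines of analysis text, one covariate, and collection of the dated pretreatment PSA values, which Appendix C does not now list. Downsides: PSA-DT will be missing for some men, adjustment does little if the values are about a week apart, and power falls for markers correlated with PSA-DT. Sample size, the PSA50 analysis and study conduct do not change.
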